5.3. Procedures for Maintaining and Breaking the Masking

N/A

6. STUDY INTERVENTION

6.1. Identity of Test Articles

The following devices will be used in this study:

Table 1: Test Articles

	Test 1	Control
Name	MiBo ThermoFlo	Bruder Moist Heat Single Eye Mask
Manufacturer	MiBo Medical	Bruder

6.2. Ancillary Supplies/Products

The following ancillary supplies will be used in this study:

Table 2: Ancillary Supplies

Ultrasound Gel	
Solution Name/Description	Aquasonic 100 Ultrasound Transmission Gel
Manufacturer	Parker Laboratories, Inc.

6.3. Administration of Test Articles

Test article will not be dispensed to subjects. Upon completion of treatment with the Bruder mask, the mask will be disposed and a new mask used per subject.

6.4. Packaging and Labeling

N/A

6.5. Storage Conditions

No samples will be collected as part of the study procedures.

6.6. Accountability of Test Articles

JJVC will provide the Investigator with sufficient quantities of study articles and supplies to complete the investigation. Test article must be kept in a locked storage cabinet, accessible only to those assigned by the Investigator for dispensing. The Investigator may delegate this activity to authorized study site personnel listed on the Site Delegation Log. All test articles must be accounted.

████████ Site Instructions for Test Article Receipt and Test Article Accountability for additional information.

7. STUDY EVALUATIONS

7.1. Time and Event Schedule

Table 3: Time and Events

Visit Information	Visit 1 Screening & Treatment
Time Point	Day 1
Estimated Visit Duration	2.5 hours
Statement of Informed Consent	x
Demographics	x
Medical History/Concomitant Medications	x
Habitual Contact Lens Information	x
Inclusion/Exclusion Criteria	x
Entrance Visual Acuity	x
Slit Lamp Biomicroscopy	x
Meibography	x
Tear Lipid Layer Measurement	x
Non-Invasive Tear Break Up Time	x
Topography	x
Eyelid Photography	x
MiBo ThermoFlo	x
Bruder Mask	x
Exit Snellen Distance Visual Acuity	x

7.2. Detailed Study Procedures

VISIT 1

Note: The subjects should present to Visit 1 wearing spectacles (if necessary), not having worn contact lenses on the day of the visit.

Visit 1: Screening		
Step	Procedure	Details
1.1	Statement of Informed Consent	Each subject must read, understand, and sign the Statement of Informed Consent before being enrolled into the study. The Principal Investigator or his/her designee conducting the informed consent discussion must also sign the consent form. Note: The subject must be provided a signed copy of this document.
1.2	Demographics	Record the subject's year of birth, gender, race and ethnicity.
1.3	Medical History and Concomitant Medications	Questions regarding the subjects' medical history and concomitant medications.

Visit 1: Screening			
Step	Procedure	Details	
1.4	Eligibility after Screening	
All responses to Screening Inclusion Criteria questions must be answered “yes” and all responses to Exclusion Criteria must be answered “no” for the subject to be considered eligible.
 
If subject is deemed to be ineligible after screening, proceed to Final Evaluation and complete Subject Disposition. Refraction and Biomicroscopy forms are not required.
	

Visit 1: Baseline			
Step	Procedure	Details	
1.5	Entrance Visual Acuity	
Record the distance Snellen visual acuity (OD, OS, and OU) to the nearest letter with their habitual correction in place (if required). Subjects must read the smallest line until at least 50% of the letters are read incorrectly.
	
1.6	Slit Lamp Biomicroscopy (White Light)	
FDA Slit Lamp Classification Scale will be used to grade the findings and determine eligibility.
 
Note: If the white light appearance of the cornea reveals significant findings which require the use of NaFl to evaluate, the subject cannot continue and proceed to F.1 Final Evaluation
 
If any of these slit lamp findings are grade 3 or higher, discontinue and complete the final examination.
	
1.7	Meibography	
Image the Meibomian glands of the upper and lower lid with the Oculus Keratograph 5.
 
If the subject displays a significant percentage of partial Meibomian glands (Grade 3 or 4 on the Pult 5-point grading scale), proceed to the subject final evaluation.
	SOP_C12_Oculus_Keratograph_V2
1.8	Eligibility after Baseline	All responses to Inclusion Criteria questions must be answered “yes” and all responses to Exclusion Criteria questions must be answered “no” for the subject to be considered eligible.	

Visit 1: Baseline			
Step	Procedure	Details	
		If subject is deemed to be ineligible after baseline, proceed to Final Evaluation and complete all forms.	

Visit 1: Treatment			
Step	Procedure	Details	
1.9	Eyelid Photography	The upper and lower eyelid margins of the subject will be photographed, OD, OS	Work Aid: Eyelid Photography
1.10	Tear Lipid Layer Thickness (LLT)	Measure the pre-treatment tear film LLT using the TearScience Lipiview, (OD, OS)	Work Aid: TearScience LipiView II Lipid Layer Thickness Measurement
1.11	Non-Invasive Tear Break Up Time (NITBUT)	Perform pre-treatment NITBUT using Oculus Keratograph 5 (OD, OS)	SOP_C12_Oculus Keratograph_V2
1.12	Corneal Topography	Perform pre-treatment corneal topography with the Oculus Keratograph	SOP_C12_Oculus Keratograph_V2
1.13	Thermography	Perform pre-treatment measurement of the external eyelid and palpebral conjunctival temperature for the upper and lower lids, (OD and OS)	SOP_C31_Thermography_V1.0
1.14	Randomization	Randomize treatment to eye using the randomization schedule	
1.15	MiBo ThermoFlo	Perform 12-minute MiBo ThermoFlo treatment on the eye indicated on the randomization schedule using the ThermoFlo Elite Eye Pad.	Work Aid: MiboFlo
1.16	Thermography	Immediately perform post-treatment measurement of the external eyelid and palpebral conjunctival temperature for the upper and lower lids, collecting data for the lower lid first.	SOP_C31_Thermography_V1.0
1.17	Bruder Mask	Heat the Bruder Mask per the manufacturer's instructions, measure the mask surface temperature and perform 10 minute Bruder Mask treatment on the contralateral eye.	Work Aid: Bruder Mask_V2

Visit 1: Treatment			
Step	Procedure	Details	
		Note: The Bruder Mask should be placed gently on the closed eyelids. Do not apply pressure on the mask and eye.	
1.18	Thermography	Perform post-treatment measurement of the external eyelid and palpebral conjunctival temperature for the upper and lower lids	SOP_C31_Thermography_V1.0
1.19	Tear Lipid Layer Thickness (LLT)	Measure the post-treatment tear film LLT using the TearScience Lipiview, OD, OS	Work Aid: TearScience LipiView II Lipid Layer Thickness Measurement
1.20	Corneal Topography	Perform post-treatment corneal topography with the Oculus Keratograph	SOP_C12_Oculus_Keratograph_V2
1.21	Non-Invasive Tear Break Up Time (NITBUT)	Perform post-treatment NITBUT using Oculus Keratograph 5 (OD, OS)	SOP_C12_Oculus_Keratograph_V2
1.22	Eyelid Photography	The upper and lower eyelid margins of the subject will be photographed, OD, OS	Work Aid: Eyelid Photography

FINAL EVALUATION

The final evaluation will ordinarily take place immediately following the last scheduled follow-up visit per the study protocol. It may also take place at any point the subject discontinues the study or is terminated from the study.

Final Evaluation			
Step	Procedure	Details	
F.1	Final Exam Form	Indicate if the subject completed the study successfully. If subject discontinued from the study, indicate the reason.	
F.2	Exit Slit Lamp Biomicroscopy (White Light)	FDA Slit Lamp Classification Scale will be used to grade the findings and determine eligibility. Note: If the white light appearance of the cornea reveals significant findings, use NaFl to evaluate.	
F.3	Snellen Exit Acuity	Record the corrected distance visual acuity to the nearest letter (OD, OS, and OU).	

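### LLT and NITBUT are read once, after both treatments, so the MiBo eye is read roughly 10 minutes or more later after its own heating than the Bruder eye; separately, step 1.18 omits the timing and lid order that step 1.16 sets

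*Combined protocol and SAP*

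**What the plan says.** All steps are in Section 7.2 of the combined protocol and SAP, under Visit 1: Treatment.

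- Step 1.14: "Randomize treatment to eye using the randomization schedule". The two sequences in Section 4.1 are left/right allocations; neither changes which treatment comes first.
- Step 1.15: 12 minutes of MiBo ThermoFlo on the allocated eye.
- Step 1.16: "Immediately perform post-treatment measurement of the external eyelid and palpebral conjunctival temperature", for upper and lower lids, "collecting data for the lower lid first".
- Step 1.17: heat the mask, take its surface temperature and "perform 10 minute Bruder Mask treatment on the contralateral eye". The step cites "Work Aid: Bruder Mask_V2".
- Step 1.18 says only to "perform post-treatment measurement of the external eyelid and palpebral conjunctival temperature for the upper and lower lids". It has no word on promptness and no lid order.
- Step 1.19: "Measure the post-treatment tear film LLT using the TearScience Lipiview, OD, OS". Corneal topography (1.20) and NITBUT in both eyes (1.21) follow.

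LLT and NITBUT each have one pre-treatment reading (1.10, 1.11) and one post-treatment reading. No interval from end of heating to reading is set.

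The synopsis calls LLT and NITBUT secondary endpoints; Sections 2.1 and 2.2 call them other observations. Section 14.5 models eyelid temperature only, Sections 14.6 and 14.7 are not applicable, and Section 14.1 promises summary tables.

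**The concern.** A contralateral design lets each subject act as their own control, provided the two eyes are read under comparable conditions. Section 1.5 says that heating could raise lipid layer thickness or break-up time transiently. For a transient effect, time since heating is part of what the endpoint means. Section 2.1 asks what one 12-minute MiBo session does to the tear film, yet the MiBo eye's delay is set by the other eye's treatment. Full compliance produces that delay in the same direction in every subject, so enrolling more subjects does not average it out.

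The thermography wording is a separate matter. A different delay or lid order in the Bruder eye would enter the MiBo-minus-Bruder temperature contrast of Section 14.5. It would also enter Other Observation 1 in Section 2.3 (Bruder against 40°C), which rests directly on the step 1.18 reading. Site staff are unmasked (Section 5.2), so equal written timing is a simple safeguard.

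**Working it through.** The plan states no figure for the gap, so there is none to reproduce.

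**Inputs from the documents**
- Bruder application: 600 s (step 1.17).
- Mask heating H: 20 s, or 30 s with both permitted 5 s reheats (Section 1.5; the appended Bruder work aid agrees).
- LipiView recording: 20 s per eye, one eye after the other (LipiView work aid, steps 13 and 14).

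**Not timed in the documents**
- U: step 1.16 thermography, plus shaking, measuring and sleeving the mask, plus any wait for it to cool. The appended Bruder work aid re-measures a hot mask every 60 s with no stated limit. Step 1.17 cites a later version of that aid, which is not among the documents, so cooling waits are not quantified.
- D: the interval between the two eyes' readings.

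**Gap between the two ends of heating:** G = U + H + 600 s.
- U = 0, H = 20 s: 620 s = 10 min 20 s.
- U = 0, H = 30 s: 630 s = 10 min 30 s.
- Mask heated in parallel with steps 1.15 or 1.16, U = 0: 600 s = 10 min 00 s.

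**Difference in time since heating at the reading:** G − D if the MiBo eye is read first, G + D if it is read second.
- U = 0, H = 20 s, D = 20 s (the LipiView video alone): 620 − 20 = 600 s (10 min 00 s), or 620 + 20 = 640 s (10 min 40 s).
- Assuming U = 60 to 300 s, D = 60 to 120 s and H = 20 to 30 s:
  - MiBo eye first: 620 + 60 − 120 = 560 s (9 min 20 s) to 630 + 300 − 60 = 870 s (14 min 30 s).
  - MiBo eye second: 620 + 60 + 60 = 740 s (12 min 20 s) to 630 + 300 + 120 = 1050 s (17 min 30 s).

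These ranges illustrate the assumptions and are not bounds. NITBUT follows the same formula with its own D. If one side were always read first and the allocation came out balanced, the D terms would cancel on average and leave G. Randomising the eye can therefore balance the reading order but not the gap.

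**Thermography wording.** Step 1.16 fixes promptness and lid order; step 1.18 fixes neither. The appended thermography SOP gives no delay and no lid order, so it does not fill the difference. Its change summary runs to version 3.0 while the steps cite V1.0. The appended Bruder work aid ends with the 10-minute application and does not fill it either.

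**The case against.** The strongest reply is that no planned inference on the tear film is harmed. Section 2.3 has no LLT or NITBUT hypothesis, Section 14 specifies no formal tear-film comparison, and Section 2.1 calls this a pilot and sets no time point. A later reading is still a post-treatment reading. All of that stands, and it limits the consequence to descriptive summaries. It does not remove the point, because those summaries are the planned output for the endpoints that the synopsis names as secondary.

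The word transient in Section 1.5 also comes without a time scale. If the effect lasts hours, ten minutes hardly matters; if minutes, it does. A reader might infer that the tear-film results are biased against MiBo. The documents do not support that: they give no time course, so neither direction nor size can be stated.

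On temperature, step 1.18 directly follows 1.17, so a prompt reading is the natural sequence, and the cited V2 work aid may say what happens after mask removal. A reader might infer that Bruder temperatures are taken late. The documents show only that unequal timing or lid order is permitted. Nor does the point reach the primary hypothesis (MiBo against 40°C), which uses only the MiBo eye's own reading.

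The present order also has a merit: both eyes are read after the same two treatment periods. Separate readings give that up.

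**Conclusion.** The point holds for the tear-film readings as a built-in timing difference. With the steps as listed, heating ends at least 10 min 20 s earlier in the MiBo eye (about 10 min with parallel mask heating), plus the untimed steps. At the reading, the difference is that gap minus or plus the interval between the two eyes' readings. This rests on the listed order and on the mask heating times in Section 1.5. The MiBo before-after change and any descriptive between-eye comparison carry the delay. No size in nm, seconds of break-up time or °C is claimed.

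The wording difference between steps 1.16 and 1.18 is a gap in specification. It bears on the Section 14.5 contrast and on Other Observation 1, with no demonstrated error. Both parts should be corrected before data collection, since times that were not recorded cannot be recovered.

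**What to change.** 1. Give step 1.18 the same instruction as step 1.16: immediate thermography, lower lid first. Record on the eCRF the time from end of heating to each thermography image and to each LLT and NITBUT reading. Reconcile the cited and appended versions of the Bruder work aid and the thermography SOP.
2. Take each eye's post-treatment LLT, topography and NITBUT at the same stated interval, and in the same order, after its own treatment: the MiBo eye after step 1.16 and before 1.17, the Bruder eye after step 1.18.

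Item 1 costs wording and a few time fields. Item 2 adds some minutes to a visit planned at about 2.5 hours, because the LipiView and Keratograph are set up once per eye instead of once for both. It lengthens the Bruder eye's interval from baseline readings to treatment. The MiBo work aid has the subject close the eyes, so the Bruder eye may be read after two closure periods and the MiBo eye after one. The randomisation list does not change.

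If item 2 is not adopted, report the recorded times and describe the LLT and NITBUT summaries as taken at unequal times since heating.

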2. STUDY OBJECTIVES, ENDPOINTS AND HYPOTHESES

2.1. Objectives

The primary study objective of this pilot study is to measure posterior eyelid temperature (palpebral conjunctiva) to determine the ability of the MiBo ThermoFlo to raise posterior eyelid temperature to levels sufficient to provide a therapeutic effect in the treatment of MGD.

Other observations in this study include testing whether the MiBo ThermoFlo treatment can induce a change in tear lipid layer thickness and/or non-invasive tear break up time after (1) 12-minute treatment session.

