System for measuring and analyzing the cornea topography, including topographic measurement, near portion height measurement, lid angle measuring, imaging, pupillometry measuring, and measuring the back surface of a contact lens.

B. Procedure: Topographic Measurement

Note: If the Keratograph is moved to a different location, position the device so that direct light cannot influence measurements. The Keratograph should be operated in a dark room to ensure that the examination is conducted without interference from reflections.

1. Switch on the PC or laptop.
2. Switch on the Keratograph at the power supply (position ON). The LED on the switch will light up in green.
3. The PC will display the Keratograph icon on the desktop. Double click to open the program.
4. The program opens to “Patient Data Management”. A patient list is displayed on the left hand side.
5. If examining a new patient, enter the patient information into the “Patient” box above the patient list. The new patient will then appear in the patient list.
6. Select the patient to be examined from the list. (Clicking [Search] provides search function by first name, last name, date of birth, or by assigned ID number.)
7. This will transfer to the patient window. A list of any previous examinations for this patient is in the examination window on the bottom right.
8. Click [Keratograph] to start the Keratograph software.
9. Select the menu “Examination”.
10. Click on “New examination (eye)”.
11. The Measuring window appears. The keratograph starts the illuminated Placido ring system automatically.
12. Clean the chin and forehead rest of the keratograph with an alcohol pad. A clean chin rest paper can also be used.
13. Position the patient in the keratograph instrument. Adjust the height of the stage so that the chin and forehead rests are comfortable for the patient. The black ring marking should be used to gauge the required height of the patient’s eyes.

UNIVERSITY of HOUSTON

THE OCULAR SURFACE INSTITUTE

Standard Operating Procedure for Oculus Keratograph 5

14. Instruct the patient to focus on the red light in the center of the Placido ring system for the whole examination.
15. Ask the patient to open his/her eye wide while looking into the red fixation spot.

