5. Under the Video tab, depending on whether a single or series of images will be captured, select either "Capture Single Image" or "Capture Image Series" (yellow arrow, Fig. 1).

Note: If "Capture Image Series" is selected, you must also specify how the images will be captured. To do this, select "Configure Series Image Capture" under the Video tab and make the appropriate selections.

Noncontact Infrared Thermography

[figure not shown]

Figure 1

6. On the monitor, you will see an active image in the upper left hand corner. Position the camera using the joystick so the area of interest is centrally located and focused (i.e., the corneal surface/precorneal tear film as indicated by the blue asterisk, Fig. 2).

Note: If thermographic images of the palpebral conjunctiva overlying the meibomian glands are to be obtained, use a Q-tip to evert the lids and to hold them into place (do not use your fingers).

7. At the upper right hand corner of the screen, use the scroll icon next to "palette" to select the output of the image (gray scale, rainbow, IR, iron, etc.). For studies within TOSI, generally select the "Rainbow" or "Gray Scale" palette from the dropdown menu in the upper right corner of the screen (green arrow, Fig. 2).

Figure 2

UNIVERSITY of HOUSTON

THE OCULAR SURFACE INSTITUTE

Noncontact Infrared Thermography

8. To the right of the image of the person in Figure 2, there are settings where you can set the maximum and minimum temperature range that you expect to find in the area of the eye you want to capture the reading. A preset setting is indicated if the box marked AGC is checked. If you want to insert your own maximum and minimum setting, deselect the AGC box and slide the max and/or min boxes up or down to adjust the ranges. You can also enter the temperatures in the gray boxes at the top (maximum temperature) and bottom (minimum) of the sliding scale figure. To measure the ocular surface temperatures, a recommended maximum and minimum setting would be 105 and 80 degrees Fahrenheit, respectively.
9. When you are ready to capture a single image or an image series click on the Camera icon  (for single image capture only) or the red recording icon  (for image series capture only) directly beneath the active image.
10. To exit the program, click on the File tab and then click "Exit".

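### NITBUT is measured before topography at baseline but after it post-treatment, so the within-eye NITBUT change may carry an order effect; swapping steps 1.20 and 1.21 removes it.

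*Combined protocol and SAP*

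**What the plan says.** The treatment table in Section 7.2 fixes the order of the tests.

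Before treatment:
- 1.10: "Measure the pre-treatment tear film LLT using the TearScience Lipiview, (OD, OS"
- 1.11: "Perform pre-treatment NITBUT using Oculus Keratograph 5 (OD, OS"
- 1.12: "Perform pre-treatment corneal topography with the Oculus Keratograph"
- 1.13: "Perform pre-treatment measurement of the external eyelid and palpebral conjunctival temperature for the upper and lower lids, (OD and OS"

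After treatment, thermography comes first (1.16 after MiBo, 1.18 after the Bruder mask), then LLT (1.19). Step 1.20 is "Perform post-treatment corneal topography with the Oculus Keratograph", and NITBUT comes at 1.21. The change of order is not explained.

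The Keratograph SOP in Appendix D gives this instruction for topography: "Ask the patient to open his/her eye wide while looking into the red fixation spot".

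Section 2.1 lists, among the other observations, "testing whether the MiBo ThermoFlo treatment can induce a change in tear lipid layer thickness and/or non-invasive tear break up time" after one 12-minute session. The Synopsis names LLT and NITBUT as the secondary endpoints. Section 2.2 lists topography with them as other observations. Sections 14.6 and 14.7 are both marked not applicable, so no model or test is specified for LLT, NITBUT or topography. Only the descriptive summaries of Section 14.1 apply.

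**The concern.** Section 2.1 asks whether MiBo changes NITBUT, which is naturally read as a before-after comparison in the MiBo eye. That comparison is clean only if the two readings are taken under the same conditions apart from treatment. Here the post-treatment reading directly follows a capture with the eye held wide open, and the baseline reading does not. If that capture alters tear-film stability for the next few minutes, the alteration appears in the change score and cannot be separated from treatment. It could run either way, imitating an effect or hiding one.

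With no analysis specified, a reader of the study report is likely to see mean NITBUT before and after by treatment and read the difference as the effect of the device.

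**Working it through.** **1. Steps side by side (Section 7.2).**

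| Test | Before treatment | After treatment |
|---|---|---|
| LLT | 1.10 | 1.19 |
| NITBUT | 1.11 | 1.21 |
| Topography | 1.12 | 1.20 |

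LLT is first of the three both times. NITBUT and topography trade places.

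**2. What the reversal can bias.** For eye j, let T(j) be the true treatment effect on NITBUT and s(j) the carry-over from a topography capture just before it.

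- Baseline NITBUT: no preceding topography, so no s.
- Post-treatment NITBUT: baseline + T(j) + s(j).
- Within-eye change: T(j) + s(j). The two terms cannot be separated.
- MiBo-minus-Bruder difference in change: [T(M) − T(B)] + [s(M) − s(B)]. If s is the same in both eyes, this is T(M) − T(B).
- With 1.20 and 1.21 swapped: s(j) = 0 at both time points.

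LLT precedes both tests each time, so the reversal contributes nothing to its change. Post-treatment temperatures (1.16, 1.18) are taken before any of these steps. The change in topography is exposed in the opposite direction: its baseline reading follows an NITBUT in which the subject keeps the eyes open as long as possible, and its post-treatment reading does not.

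**3. Size.** The plan gives no SD, effect size or power for NITBUT, and Section 14.2 says no formal sample size calculation could be done. There is no figure to reproduce. The following is an illustration under an assumed shift.

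Let d be s divided by the SD of the change score, with no true treatment effect. A two-sided 5% paired t-test on n subjects rejects with probability P(|t′| > t(0.975, n−1)), where t′ is noncentral t with n−1 degrees of freedom and noncentrality d√n. For example, n = 12 and d = 0.25 give 0.25 × √12 = 0.87. The values of n are the minimum number completing (12) and the enrollment target (20).

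| Assumed d | n = 12: d√n | Rejects | n = 20: d√n | Rejects |
|---|---|---|---|---|
| 0 | 0 | 5.0% | 0 | 5.0% |
| 0.1 | 0.35 | 6.2% | 0.45 | 7.1% |
| 0.25 | 0.87 | 12.4% | 1.12 | 18.6% |
| 0.5 | 1.73 | 35.3% | 2.24 | 56.5% |
| 1.0 | 3.46 | 88.3% | 4.47 | 98.9% |

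A simulation of 40,000 trials per setting gave the same shift to both eyes (assumed between-eye correlation 0.5; d of 0.25, 0.5 and 1.0). The between-eye difference in change was rejected in 4.9% to 5.1% of trials, in line with the algebra in step 2.

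**The case against.** The case for leaving the order alone is fair. Nothing in the documents shows that topography affects the next NITBUT. The SOP has topography fire automatically once the eye is aligned, and has NITBUT start after two prompted blinks, which may well reset the tear film. This is a pilot, the tear-film question is an other observation, and no test of it is planned. The randomized fellow eye goes through the same two steps in the same order, so a common shift drops out between eyes.

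All of this limits the weight of the point, and none of it explains the reversal. The between-eye contrast answers a different question (MiBo against Bruder) from the one in Section 2.1, and no section directs the analyst to it for NITBUT.

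Three stronger readings are tempting, and the documents do not support them.

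- *That baseline tear-film tests are free of lid eversion and post-treatment ones are not.* The Thermography SOP does say to "use a Q-tip to evert the lids and to hold them into place" for conjunctival images, and thermography precedes the tear-film tests only after treatment. But meibography of both lids (1.7) comes before the baseline tests, and its SOP also everts the lid. Only a difference in timing or number of eversions could matter. Thermography at 1.16 must also be immediate, so it cannot be moved behind the tear-film tests.
- *That the LLT change is biased too.* LLT is the first tear-film test at both time points, so the reversal cannot reach it.
- *That pre-treatment thermography (1.13) should move ahead of LLT (1.10) to match the order fully.* This would put three tests between the baseline of the primary temperature endpoint and treatment; at present 1.13 is the last measurement before randomization. Nor would it match the MiBo eye. Baseline LLT would follow eversion almost at once. After treatment, the MiBo eye is everted at 1.16 and then waits through the 10-minute mask (1.17) and thermography (1.18, taking that step as the Bruder eye, which it does not name) before LLT at 1.19.

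**Conclusion.** The point holds in a narrow form. NITBUT and topography are reversed between baseline and post-treatment without explanation, and any topography carry-over is confounded with treatment in the within-eye NITBUT change. The documents give neither evidence for such a carry-over nor its size. The rejection rates above rest on an assumed additive shift and a paired test that the plan does not specify. At a shift of 0.1 SD the inflation is slight (6.2% to 7.1%); at 0.5 SD it would be serious (35.3% to 56.5%). The MiBo-minus-Bruder difference in change is protected if the shift is equal in both eyes. This is a low-priority point, worth acting on because the correction is simple.

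**What to change.** In Section 7.2, swap steps 1.20 and 1.21 so that post-treatment NITBUT precedes topography. The order is then LLT, NITBUT, topography at both time points. Leave pre-treatment thermography at 1.13. The cost is renumbering two steps: no added test, subject or visit time, and Table 3 needs no change because it lists each test once without separating before from after.

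If the present order is kept, state the reason, and base any conclusion about NITBUT on the between-eye difference in change, noting that it assumes the same order effect in both eyes.
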